3.4.2 Off-label use

These outcomes will be ascertained using AUPD or the Danish National Registry of Patients in Denmark and using the GPRD's Event File or Drug File in the UK. Off-label use will be defined as prescription of rosiglitazone dispensed by/issued to:

- Patients aged 16 years or younger at the time of any rosiglitazone prescription;
- Patient with concomitant use of insulin, defined as at least one prescription for insulin in between the first and last prescription for rosiglitazone²;
- Patients diagnosed with type 1 diabetes mellitus;

- Women with gestational diabetes without evidence of pre-gestational diabetes (UK only);
- Women with polycystic ovary syndrome (UK only)

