The present study was commissioned by the European Medicines Agency (EMA), following the suspension of rosiglitazone preparations in the European Union. EMA wishes to retrospectively examine the impact of risk minimisation actions in the European Union (such as warnings, scientific publications, and regulatory decisions) on utilization of rosiglitazone and on the condition of rosiglitazone-using patients with type 2 diabetes (the target population).

2 Specific aims

The specific aims of this study are as follows:

- To describe trends in patterns of utilisation of rosiglitazone-containing preparations over time, in particular, in response to external events, such as scientific and media publications, EMA's press releases, or EMA's regulatory decisions aimed at risk minimisation;
- To examine the extent of use of rosiglitazone-containing preparations in persons with potential contraindications;
- To examine the extent of use of rosiglitazone-containing preparations in persons outside the primary indication (off-label use);
- To examine risk of acute drug reactions among patients who switch from alternative antidiabetic therapies to rosiglitazone preparations or vice versa;
- To examine glycaemic control and other objective parameters of disease among patients who switch from alternative antidiabetic therapies to rosiglitazone preparations or vice versa.

3 Methods

3.1 *Setting and study population*

This study will be conducted in Denmark and in the United Kingdom (UK).

In Denmark, the source population includes residents of the country's North and the Central regions, with combined population of about 1.8 million, or approximately 33% of the population. Denmark is a welfare state, with universal, tax-funded access to all medical services, including reimbursement for prescribed medicine. Many medical services rendered in Denmark have been routinely and prospectively recorded, on patient level, for the past several decades in population registries; data linked from these registries will be used in the present study.¹⁴

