In the UK, the study will be conducted based on data from the General Practice Research Database (GPRD). The GPRD is an ongoing longitudinal database that collects data from over 350 general practices in the UK since 1987. The UK provides a unique medical environment to create a computerized medical data resource for medical epidemiological research for two main reasons: a) the primary health care system comprehensively covers the UK population; b) the information on all relevant medical care is located in the offices of the general practitioners (GPs), who function as "gatekeepers" for hospital and specialist referrals in the UK health system. The GPRD contains information on more than 6 million patients, of whom 3.5 million are currently registered, and a

cumulative follow-up time of more than 40 million person-years. It covers 6% of the UK population; this sample is representative with respect to age, gender and race/ethnicity distribution.

The study population will include, in both countries, diabetic patients treated with oral glucose lowering drugs between 1 January 2000 and 1 January 2011. This period covers the time from the approval of rosiglitazone for use in the European Union, in July 2000, until the decision by the European Medicines Agency to suspend the drug, on 23 September 2010. The study period also includes a pre-approval and a post-suspension periods to allow examination of drug utilization patterns in response to these events.

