3.6.2 Contraindications for use and off-label use

Prevalence of contraindicated or off-label use will be examined according to calendar time, where events marking relevant scientific publications and regulatory decisions will be marked. We will

report the number and proportion of patients prescribed rosiglitazone who had a diagnosis consistent with a contraindication for rosiglitazone use or with off-label use as defined in the Methods. We will provide the proportions in each country and over time. We will follow the analytic methods described above, provided that the sample size is large enough. At a minimum, use by patients with the additional contraindications (ischemic heart disease and/or peripheral vascular disease) listed in the 2008 press release¹⁰ will be examined in the periods before and after the publication of the press release including any prior diagnosis of liver disease, ischemic heart disease, cardiac failure, or acute coronary syndrome.

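### Three off-label rules in section 3.4.2 count women within the indication and insulin that does not overlap, and the insulin flag cannot be dated to a calendar month

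*Protocol*

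**What the plan says.** The third aim in Protocol section 2 is "To examine the extent of use of rosiglitazone-containing preparations in persons outside the primary indication (off-label use". Section 1 describes the people of interest as "rosiglitazone-using patients with type 2 diabetes (the target population".

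Section 3.4.2 then lists five grounds for calling a rosiglitazone prescription off-label. Three matter here:

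- PCOS: "Women with polycystic ovary syndrome (UK only".
- Gestational diabetes: "Women with gestational diabetes without evidence of pre-gestational diabetes (UK only".
- Concomitant insulin: "defined as at least one prescription for insulin in between the first and last prescription for rosiglitazone".

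Section 3.6.2 says that "Prevalence of contraindicated or off-label use will be examined according to calendar time", with publications and regulatory decisions marked. It takes the definitions over from the Methods and, if numbers allow, applies the methods of section 3.6.1: four periods, calendar months and a sliding four-month window.

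On who is studied, section 3.1 says "The study population will include, in both countries, diabetic patients treated with oral glucose lowering drugs". Section 3.3 enters people on two or more prescriptions for such drugs and mentions no diagnosis.

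**The concern.** A rule for this aim has to do two things. It has to separate use outside the indication from use within it, and it has to say when the use happened, because the result is plotted against regulatory milestones.

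The two diagnosis items can fail the first test: they flag a woman for a condition she has or had, even when she also has the type 2 diabetes for which the drug is indicated. The insulin item can fail both. It labels a person over an interval set by two rosiglitazone dates, whether or not the two drugs were taken together, and the label may depend on prescriptions years later.

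At stake are the level of off-label use and, for insulin, whether its course around the milestones can be read at all.

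**Working it through.** The protocol gives no figure on this point, so the check sets each rule beside the aim and the planned analysis.

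**1. PCOS.** The item has one condition, the diagnosis. It does not ask whether type 2 diabetes is present and gives no date. A woman with both conditions who receives rosiglitazone for her diabetes is inside the indication under section 2 and off-label under section 3.4.2.

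**2. Gestational diabetes.** The qualifier covers diabetes before the pregnancy. A woman with gestational diabetes, then type 2 diabetes, then a first rosiglitazone prescription years afterwards has no pre-gestational diabetes, so she is flagged. Nothing ties the prescription to the pregnancy.

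**3. Insulin.** Hypothetical histories put through the literal rule:

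| History | Flagged? | Drugs used together? |
|---|---|---|
| Rosiglitazone 2002–03, insulin once in 2005, rosiglitazone again 2008 | Yes | No |
| Rosiglitazone 2002–09, insulin added 2008 | Yes | Only from 2008 |
| Long-term insulin, one rosiglitazone prescription | No: the interval has zero length (unless same-day insulin counts) | Yes |
| Insulin issued shortly before the first or after the last rosiglitazone prescription, supply overlapping | No | Yes |

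The third history can occur: section 3.3 requires two prescriptions for oral glucose-lowering drugs, not two for rosiglitazone. In the second, status in any month before 2008 cannot be settled without the 2008 record, and the rule does not say to which months the flag belongs.

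**4. Longest insulin interval.** From 1 July 2000 (EU introduction, section 3.6.1) to 23 September 2010 (suspension, section 3.1) is 3,736 days; 3,736 / 365.25 = 10.2 years.

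**5. Does other text narrow the rules?** No. Section 3.6.2 adds no condition. Section 3.4 refers to Appendix 1 for codes, but its UK lists have no PCOS or gestational diabetes section. Other rules do carry a time anchor: age in section 3.4.2 is taken at a rosiglitazone prescription, and contraindications in section 3.4.1 must precede the first one.

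**6. Illustrations of size (assumed rates).**

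- Diagnosis items: UK users × share who are women × share of those women with type 2 diabetes plus a PCOS or past gestational diabetes code. The 20,000 users come from section 4; the shares of 40–50% and 0.5–3% are assumptions. Low: 20,000 × 0.40 × 0.005 = 40 (0.2%). High: 20,000 × 0.50 × 0.03 = 300 (1.5%).
- Insulin item: if isolated insulin prescriptions without true co-use occur at a constant rate r per year (assumed 0.5–2%), the share wrongly flagged over T years is 1 − exp(−rT). This gives 0.5–2.0% for 1 year, 2.5–9.5% for 5 years and 5.0–18.5% for 10.2 years. The point is the direction: the chance of a false flag grows with length of use.

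**The case against.** The case for leaving the rules alone has some force.

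- **The diagnoses are proxies.** Section 3.6.2 treats them as compatible with off-label use in a descriptive analysis, and both items are UK only. That limits the damage to the overall figure. It does not help the two items themselves: they target rare uses, so women within the indication could dominate them.
- **The gestational item may mean a current pregnancy.** On that reading most of the problem disappears, but the text sets no such limit.
- **The insulin rule is a house convention.** Section 3.5 defines other concomitant medication by the same first-to-last interval. There it supplies a covariate; here it is an outcome followed through calendar time, which asks more of it.
- **A statistical analysis plan could settle how the flag is placed in months.** It could, but the definition is already fixed in the protocol and would have to be changed, not just supplemented.

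Three stronger readings are tempting and not supported:

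- **Women with PCOS and no diabetes are shut out by entry.** Section 3.1 speaks of diabetic patients, but section 3.3 enters by prescription and section 3.6.2 counts patients prescribed rosiglitazone. The two entry descriptions need aligning; exclusion is not shown.
- **Every month before insulin began will be back-dated as off-label.** This is a likely result of applying the rule literally, but no section states it.
- **The insulin rule overstates use about 1.9-fold.** With insulin added at an assumed 3–8% a year over 4 years, 11.3–27.4% are ever flagged against a mean concurrent share of 5.8–14.4%. That compares ever-use with average point prevalence. Everyone flagged in that model really did add insulin while on rosiglitazone, so it shows no misclassified patient.

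**Conclusion.** The point holds as an error in stated rules. Taken literally, the PCOS and gestational diabetes items count women who have type 2 diabetes and are, on that criterion, within the indication. The insulin item counts non-overlapping use, cannot capture a user with a single rosiglitazone prescription, and yields a patient-level flag that depends on later prescriptions and so cannot validly be placed in calendar months as section 3.6.2 requires.

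The size is unknown. The 0.2–1.5% of UK users and the insulin percentages rest wholly on assumed rates, so the documents do not establish that the published level or trend would be materially wrong. Whether insulin co-use belongs among the off-label criteria is a labelling question and is not judged here. The change is worth making before analysis because it is cheap and because off-label use is one of the five aims.

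**What to change.** Amend section 3.4.2 so that each criterion is assessed at the date of each rosiglitazone prescription:

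- **PCOS and gestational diabetes:** count only when there is no type 2 diabetes record by that date, allowing a short pre-specified grace period for late coding. The UK diabetes list in Appendix 1 mixes non-specific with type 2 codes, so state which of them qualify, and add the missing PCOS and gestational diabetes codes.
- **Insulin:** call it concomitant when an insulin prescription falls within a pre-specified fixed window around a rosiglitazone prescription, and count it in calendar time only from when it occurs. Both databases hold prescription dates. Overlap of days' supply is less practical in Denmark, where section 6.1 lists drug code, dispensing date and product number but no dosing instructions.
- **Entry:** align the diabetic-patients wording in section 3.1 with prescription-based entry in section 3.3.

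The cost is rewording and minor reprogramming on data already held. The window length has to be chosen, so a sensitivity analysis with other lengths is needed. Late or missing diabetes codes will leave some misclassification, and the reported counts for the two diagnosis items will probably be smaller.

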3.4.3 Acute drug reactions

Both acute and pre-existing events will be identified in the Danish National Registry of Patients and in the Registry of Causes of Death in Denmark and in the GPRD's Event file, in the UK.

Acute drug reactions will be defined as new (first-onset) events occurring 45 days after the date of the switch to or from a rosiglitazone preparation. We will use prior hospitalization records to screen out prevalent/prior events and conditions. The exact distribution of events that may represent a potential acute drug reaction is unknown until data analysis. We will rank all recorded new events in the order of seriousness and potential of representing an acute drug reaction. Since cardiovascular side effects are a major safety concern for rosiglitazone, as a minimum, we will examine the following events:

- All-cause mortality;
- Cardiovascular mortality;
- Acute myocardial infarction;
- Cerebrovascular accident/ischemic stroke
- Pulmonary embolism;
- Deep vein thrombosis.

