3.2 Study design

The study objectives will be addressed using cohort design based on individual-level data linkage. The design will take advantage of existing records that will have accumulated over decades, and is therefore a retrospective cohort design. Measurement and recording of exposure (prescription for oral glucose lowering medication) precedes measurement and recording of the study outcomes (e.g., acute reactions, changes in laboratory parameters).

Because of concerns over the cardiovascular safety of rosiglitazone, it would be unethical to use an experimental study to address the study objectives. Furthermore, while experimental studies answer the question about drug efficacy and safety in carefully selected and closely observed patient populations, observational studies are better suited for evaluation of the drugs' 'real-world' utilization and safety.¹⁵ A cohort study based on linkage of population-based routine records has the advantage of avoiding selection bias that could ensue in a cohort study with routine data collection if patients self-selected to participate or to drop out of the study.

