3.6.3 Acute drug reactions

For patient-level endpoints, baseline will be defined as the recorded date of medication switch/addition (as reflected by a new dispensation/issue); date of the first-time prescription dispensation/issue (in first-time users) or 1 January 2000 (in prevalent users).

We will examine the number of potential drug reactions occurring within 45 days of baseline and calculate the 45-day cumulative incidence of acute drug reactions, overall and diagnosis-specific (if the data set is large enough); We will estimate risk ratios for the acute drug reactions identified using regression, while adjusting for confounding.

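### The first-onset screen cannot apply to death and comorbidity is dated to enrolment, so the 45-day mortality ratio may be confounded by the illness that prompted the switch

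*Protocol*

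**What the plan says.** Section 3.4.3 defines acute drug reactions as "new (first-onset) events occurring 45 days after the date of the switch to or from a rosiglitazone preparation". The minimum list of events opens with "All-cause mortality", followed by cardiovascular mortality and then four diagnoses: infarction, stroke, pulmonary embolism and deep vein thrombosis. On illness that was already present, the section says "We will use prior hospitalization records to screen out prevalent/prior events and conditions". It gives no look-back length and no separate rule for death.

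For patients who change treatment, section 3.6.3 sets time zero: "baseline will be defined as the recorded date of medication switch/addition". It will "calculate the 45-day cumulative incidence of acute drug reactions, overall and diagnosis-specific", and then: "We will estimate risk ratios for the acute drug reactions identified using regression, while adjusting for confounding". The comparison group for those ratios is not named.

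Section 3.5 takes baseline comorbidity from hospital diagnoses in the ten years before study enrolment and summarises it with the Charlson index. Sections 3.3 and 3.6.1 make a person a switcher only after two prescriptions for the new therapy. On time order in general, section 3.2 says: "Measurement and recording of exposure (prescription for oral glucose lowering medication) precedes measurement and recording of the study outcomes".

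**The concern.** A serious new illness can lead to a change of treatment and also, within weeks, to death. The change of treatment then comes before the death in the records without having caused it. The recording order described in 3.2 does not help here, because the fatal illness came before the new prescription.

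Heart failure, acute coronary syndrome and infarction are among the contraindication conditions in 3.4.1, and 3.6.1 marks January 2008 as the date when contraindications were added. It is therefore plausible, though the protocol does not say so, that such illness is one reason for leaving rosiglitazone. The sponsor commissioned the study to judge the effect of its risk-minimisation actions. A mortality ratio that partly reflects the illness behind the switch could be read as an effect of starting or withdrawing the drug.

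**Working it through.** The protocol states no event rate, power or mortality ratio, so there is no figure to reproduce. The check has two textual steps and two illustrations.

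**1. The screen against the endpoints.** For the four listed diagnoses, a hospital record of the same diagnosis before the switch can remove the patient from the first-onset count. For the two death endpoints no such record can exist. The sentence also mentions prior conditions. If that meant excluding everyone with earlier disease from the mortality count, it would be a large restriction, and the protocol states it nowhere. How the screen applies to death is undefined.

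**2. The covariate date against time zero.** Time zero for a switcher is the switch date; the comorbidity look-back ends at enrolment. The protocol gives no date for enrolment. If it is taken as 1 January 2000 for prevalent users (their baseline in 3.6.3), a patient who leaves rosiglitazone on 23 September 2010 has 10 years and 265 days between the end of the look-back and the switch. An admission in that interval is not in the index. If enrolment is instead read as the switch date, the admission is included, but the index does not separate last week from nine years ago.

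**3. Direction and size of crude mortality (all inputs assumed).** Let f be the share of switchers admitted just before the switch (2% to 20%), RR their relative risk of death in 45 days (2 to 10), and t the day of the second prescription (0 to 90).

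- Effect of recently admitted switchers: 1 + f(RR − 1).
- Share of deaths still countable if a switcher must live to the second prescription, at constant hazard: max(0, 1 − t/45). This is 0.69 at day 14, 0.38 at day 28, 0.33 at day 30, and 0 from day 45.
- Net multiplier: the product of the two.

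| f, RR | t = 0 | t = 14 | t = 28 | t = 30 | t ≥ 45 |
|---|---|---|---|---|---|
| 2%, 2 | 1.02 | 0.70 | 0.39 | 0.34 | 0 |
| 10%, 5 | 1.40 | 0.96 | 0.53 | 0.47 | 0 |
| 20%, 10 | 2.80 | 1.93 | 1.06 | 0.93 | 0 |

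For example, with f = 10%, RR = 5 and t = 14: 1 + 0.10 × 4 = 1.40, and 1.40 × 0.689 = 0.96.

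**4. The ratio depends on the comparator.** If both groups are switchers with the same refill timing (before day 45), the survival share cancels. The spurious ratio is then [1 + f1(RR − 1)] / [1 + f0(RR − 1)], where f1 is the share in the index group and f0 the share in the comparator. With RR = 5:

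- f1 = 10%, f0 = 2%: 1.40/1.08 = 1.30
- f1 = 2%, f0 = 10%: 1.08/1.40 = 0.77
- f1 = f0: 1.00

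For contrast, take a comparator with no recent admissions, no two-prescription rule and no adjustment. Assume 3% annual mortality, so the 45-day risk is 1 − 0.97^(45/365.25) = 0.003746.

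- If 2% were recently admitted and 5% of them die: 0.02 × 0.05 + 0.98 × 0.003746 = 0.00467, a ratio of 1.25.
- If 5% were recently admitted and 10% of them die: 0.05 × 0.10 + 0.95 × 0.003746 = 0.00856, a ratio of 2.28.

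**The case against.** The strongest reply is that the plan already has two protections: the screen covers conditions as well as events, and 3.6.3 commits to adjustment for confounding. The Charlson codes in Appendix 1 include infarction and heart failure, and 3.5 adds nitrates, diuretics, antiplatelets and antihypertensives. Which variables enter the model is commonly left to a statistical analysis plan. This stands to the extent that the screen is not the only safeguard. It does not close the gap, because the protocol itself ties comorbidity to enrolment. The co-medications are recorded at any time between the first and last glucose-lowering prescription, so they do not date an acute illness either. The control for time since a triggering event in 3.6.4 concerns publications and agency warnings, not the patient's own illness.

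The second reply is that a patient who falls ill, switches and dies within about three weeks would usually not reach a second prescription, and so would not count as a drug-to-drug switcher. That is correct, and it pulls observed mortality down. It is a separate distortion, not a remedy. It largely cancels between switcher groups with similar refill timing. It also cannot apply to those who stop all antidiabetic drugs, whom 3.6.1 counts as switching.

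Third, 3.2 describes cohort ordering in general and is not offered as protection against confounding by the reason for switching. That is fair; the point does not depend on it.

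**Conclusion.** The gap is real, but its consequence is open. The first-onset screen cannot apply to all-cause or cardiovascular death. The adjustment planned in 3.6.3 may miss an acute admission that prompted the switch, because the comorbidity look-back is anchored to enrolment. The 45-day mortality risk ratio may therefore be confounded by that illness.

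A reader might go further and infer that post-switch mortality is inflated by reverse causation, or that the spurious ratio lies between about 1.25 and 2.3. The documents do not support either. That range is arithmetically correct but rests wholly on assumed rates, an admission-free comparator, no adjustment and no two-prescription rule. Once any of these is relaxed, the distortion can shrink, vanish or reverse. Nor does the text say that such deaths must be counted as reactions; it leaves their handling undefined. Direction and size cannot be determined from this protocol, and the point is best treated as a cheap improvement.

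**What to change.** 1. In 3.5 and 3.6.3, measure comorbidities for the patient-level endpoints up to the baseline date, which for switchers is the switch date, instead of up to study enrolment.
2. In 3.6.3, flag any hospital admission or hospital diagnosis in the 45 days before baseline, using the Danish National Registry of Patients and the GPRD Event File, in switchers and comparators alike. Report 45-day all-cause and cardiovascular mortality with and without the flag. Give the risk ratio restricted to unflagged patients as a sensitivity analysis alongside the full-cohort ratio. The full cohort should keep the main ratio, because the stated aim covers patients who switch in general and the restriction removes the sickest of them.

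The 45-day look-back simply mirrors the outcome window; the documents supply no value for it.

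The cost is one derived variable, one extra table and fewer events in the restricted analysis. Admission dates will be less precise in the GPRD, where section 6.2 has GPs entering hospital diagnoses and learning of hospital care by letter. The fix does not address the early deaths removed by the two-prescription rule.
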